# Controls for risk factor analysis:

- 1. Medical encounter and during the same month as their matched myocarditis case (index date for control select date closest to matched myocarditis case if ≥1 date/encounters are present)
- 2. At least 365 days of enrollment or activity in the EHR prior to index
- 3. No evidence of myocarditis prior to the index date
- 4. Details of matching criteria will be provided in the SAP

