#### 9. RESEARCH METHODS

#### 9.1. Study design

This is a NI, observational, retrospective cohort study utilizing a nested case-control design with secondary data collection. The broader cohort for this study is the Optum EHR database during the proposed study period of 01 January 2010 to most recent available at the time of start of data

[figure not shown]
collection (31 March 2023). This study period has been chosen to reflect the most current and complete data in the Optum database, with sufficient baseline time to examine risk factors for patients with myocarditis in each of the cohorts with index dates of 2016-later.

**Figure 1** summarizes the overall study design. Among the overall Optum EHR study population, the following mutually exclusive cohorts and index dates will be defined to address the study objectives:

- Cohort 1 Post-mRNA COVID-19 vaccination myocarditis cohort: first date of a
  myocarditis diagnosis code within 21 days after vaccination from 11 December 2020 to most
  recent data available, allowing for at least 30 days pre or post index myocarditis diagnosis for
  medical notes to confirm diagnosis through end of study period.
- Cohort 2 Post-SARS-CoV-2 infection myocarditis: first date of a myocarditis diagnosis code within 8 weeks after a positive SARS-CoV-2 test from 01 January 2020 to most recent data available, allowing for at least 30 days pre or post index myocarditis diagnosis for medical notes to confirm diagnosis through end of study period.
- Cohort 3 Pre-COVID myocarditis: most recent date of a myocarditis diagnosis from 01 January 2016 to 01 November 2019, allowing for at least 30 days pre or post index myocarditis diagnosis for medical notes to confirm diagnosis through end of study period.
- Controls for the multivariable risk factor analysis, a random sample of matched patients
  without myocarditis will be selected, e.g. with an encounter date within the same month as
  the index date for the myocarditis case, and with a similar amount of follow-up time from
  entry into the cohort and activity in the database. Additional matching criteria may be
  determined, and details of the matching methods and appropriate modeling considerations
  will be provided in the SAP.

Additional details on index dates and episode definitions will be provided in the SAP.

Figure 1. Study Design

- Censored at minimum of myocarditis diagnosis, death, disenrollment, or end of the study period

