# **Myocarditis cases:**

- 2. Diagnosis of myocarditis identified using ICD codes in EHR and/or claims when available. (ICD codes will be provided in the SAP)
- 3. At least one myocarditis inpatient record or two myocarditis records of any type dated greater than or equal to 30 days apart
- 4. Myocarditis diagnosis date between 01 January 2016 most recent EHR data available (31 March 2023)
- 5. At least 365 days of enrollment or activity in the EHR prior to the index myocarditis diagnosis.

Myocarditis cases meeting the above criteria will be divided into the following three cohorts with their own unique inclusion criteria:

- a) Cohort 1 Post- mRNA COVID-19 vaccine myocarditis cases:
  - 1. Myocarditis diagnosis date 11 December 2020 or later
  - 2. Record of mRNA vaccination within 21 days prior to the myocarditis diagnosis without a record of SARS-CoV-2 positive test within 8 weeks prior to myocarditis diagnosis
  - 3. Availability of medical notes to use for confirmation of myocarditis post-mRNA COVID-19 vaccination thirty days before or after the index event
- b) Cohort 2 Post- SARS-CoV-2 infection myocarditis cases:
  - 1. Myocarditis diagnosis date 01 January 2020 or later
  - 2. Record of SARS-CoV-2 positive test within 8 weeks prior to myocarditis diagnosis, with no record of mRNA COVID-19 vaccination during that time
  - 3. Availability of medical notes to use for confirmation of myocarditis post-SARS-CoV-2 infection thirty days before or after the index event
- c) Cohort 3 Pre-COVID-19-era acute/viral myocarditis cases:
  - 1. Most recent Myocarditis diagnosis date prior to 01 November 2019
  - 2. Availability of medical notes to use for confirmation of myocarditis within thirty days before or after the index event

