#### 9.9. Limitations of the research methods

This study has several strengths. First, it is a population-based study in a real-world population, increasing generalizability and external validity. Second, the Optum EHR database has both inpatient and outpatient data, in addition to laboratory data and microbiology results for a subset of patients that could be leveraged. In addition, the large sample size will enable the capture of a range of pre-specified health outcomes and clinical conditions, while the longitudinal nature of the data will allow us the ability to track risk factors, clinical manifestations, and changes in prognostic laboratory values over time.

However, the study also has several limitations. As is the case in any study based on secondary data sources, outcome misclassification is a possibility, as delayed and misdiagnosis of myocarditis is potentially high. However, the validation sub-study, which is being conducted concurrently, will allow us to evaluate potential misclassification of myocarditis, as well as key risk factors of interest. Diagnostic codes may also be incorrect or may be included as part of the diagnostic rule-out process or a record of a historical myocarditis event rather than an indication of a recent myocarditis, however by incorporating a multi-tier treatment and diagnostic algorithm to identify myocarditis, it will allow us to evaluate the robustness and accuracy of cases identified based on diagnosed criteria alone versus criteria that requires additional data such as medication or procedures for verification of

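### Controls must be free of earlier myocarditis but cases need not be, so recoded old disease can enter the ICD-based risk-factor models and one patient can qualify for two cohorts

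*Protocol*

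**What the plan says.** Controls (section 9.2.1) must have "No evidence of myocarditis prior to the index date".

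Cases (section 9.2.1) must meet a coding rule, "At least one myocarditis inpatient record or two myocarditis records of any type dated greater than or equal to 30 days apart", and an observability rule, "At least 365 days of enrollment or activity in the EHR prior to the index myocarditis diagnosis". Cohort 1 adds "Record of mRNA vaccination within 21 days prior to the myocarditis diagnosis without a record of SARS-CoV-2 positive test within 8 weeks prior to myocarditis", and Cohort 2 adds "Record of SARS-CoV-2 positive test within 8 weeks prior to myocarditis diagnosis, with no record of mRNA COVID-19 vaccination during that time". None of these mentions earlier myocarditis. The only exclusion criterion (section 9.2.2) concerns the length of recorded activity.

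Index dates (section 9.1): Cohort 2 uses the "first date of a myocarditis diagnosis code within 8 weeks after a positive SARS-CoV-2 test from 01 January 2020" onward. Cohort 1 is worded in the same way for 21 days after vaccination. Cohort 3 uses the "most recent date of a myocarditis diagnosis from 01 January 2016 to 01 November 2019". The same section calls the three cohorts mutually exclusive.

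The notes to Figure 1 end follow-up at the earliest of several events, one of which is a myocarditis diagnosis, and describe controls as risk-set matched. Section 9.9 concedes that a code may be a "record of a historical myocarditis event rather than an indication of a recent myocarditis".

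**The concern.** In a nested case-control study, cases and controls should come from the same population at risk. Here people with earlier myocarditis are removed from the controls but can remain among the cases. Section 9.3 lists earlier comorbidities, treatments and procedures, cardiac ones included, as medical history, and section 9.7 lets candidate risk factors be chosen stepwise or by univariate significance. Heart failure, cardiomyopathy or cardiac drugs that follow an old episode could then be selected as risk factors for the new one, because only the case group can carry that history.

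Cohort 3 has a related problem. When the index is the latest code, care given after the first episode can be counted as history before diagnosis.

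Also at stake are whether a Cohort 1 or 2 case began after its exposure, and whether comparisons between cohorts use separate patients.

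**Working it through.** The protocol gives no figure for this point, so there is nothing to reproduce. The check has two parts: the criteria applied to hypothetical patients, and an illustration of size.

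**1. The two-record rule.** Two records at least 30 days apart cannot both lie inside a 21-day window. A Cohort 1 case who qualifies on two records therefore has one outside the window, and nothing requires it to follow the dose. In Cohort 2 both can lie inside 56 days (8 weeks), but they need not.

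**2. Criteria applied to hypothetical patients.** All are assumed to have activity from 2012 and notes available. Columns I and II take Cohorts 1 and 2 at the first code *in the window*. Column I reads Cohort 3's *most recent* as latest within 2016-2019, and column II as latest ever. Column III takes Cohorts 1 and 2 at the *first-ever* code; where two entries are shown, they follow the two Cohort 3 readings.

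| Patient | I | II | III |
|---|---|---|---|
| A. 2018 inpatient; outpatient code 5 days after a 2021 dose | 1 and 3 | 1 | 3 / none |
| B. 2014 inpatient; outpatient code 5 days after a dose | 1 | 1 | none |
| C. Outpatient codes in 2018 and 10 days after a dose | 1 and 3 | 1 | 3 / none |
| D. Inpatient November 2020 after a positive test; outpatient code 5 days after an April 2021 dose | 1 and 2 | 1 and 2 | 2 |
| E. Inpatient March 2021; dose in April; outpatient code 5 days later | 1 | 1 | none |
| F. 2018 inpatient; code 3 weeks after a 2022 positive test | 2 and 3 | 2 | 3 / none |
| G. One code, with a dose and a positive test both shortly before it | none | none | none |

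Patient G shows that Cohorts 1 and 2 do exclude each other around a single diagnosis date. Patient D shows that they do not at patient level. Overlap with Cohort 3 disappears in column II, but old disease still enters Cohorts 1 and 2. Only a first-ever rule removes both problems.

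**3. Size, by illustration.** The protocol supplies only the feasibility counts in section 9.5: 240, 1,730 and 7,200. Every other input here is assumed.

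- Recoded patients = 7,200 × share with a recorded dose × share recoded within 21 days. Low: 7,200 × 0.20 × 0.005 = 7.2, and 7.2/240 = 3%. High: 7,200 × 0.50 × 0.02 = 72, and 72/240 = 30%.
- A different set of assumptions, 7,200 × share still active × share with a recorded dose × coded visits per year × 42/365 (two doses of 21 days), gives 7,200 × 0.3 × 0.2 × 0.1 × 42/365 = 5.0 (2%) up to 7,200 × 0.6 × 0.4 × 0.5 × 42/365 = 99.4 (41%).
- For a comorbidity with true odds ratio 1, prevalence 5% in controls and q in old myocarditis, and recoded share s, case prevalence is p = (1 − s) × 0.05 + s × q. With s = 0.05 and q = 0.30, p = 0.0625 and OR = (0.0625/0.9375)/(0.05/0.95) = 1.27. With s = 0.20 and q = 0.50, p = 0.14 and OR = (0.14/0.86)/(0.05/0.95) = 3.09.

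**The case against.** The strongest reply is that the design already means incident cases. Under the Figure 1 censoring note, someone with myocarditis in 2018 has left follow-up and cannot be a 2021 case, and risk-set matching points the same way. Section 9.2.2 and Table 1 also refer to a first myocarditis code or date. This stands as evidence of intent. But the note is not carried into section 9.2.1, and it cannot be squared with a most-recent index for Cohort 3. Section 9.2.2 ties its first code to the cohort criteria, and Table 1 lists the qualifying date separately from the first diagnosis date.

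A second reply is that a lone follow-up code after a dose would not qualify. Under the wording it does: the old record and the new one are two records more than 30 days apart.

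Third, section 9.1 leaves index-date and episode details to the SAP. An episode definition could indeed separate new from old disease. However, the control rule and the case criteria are already fixed in the protocol, and the mismatch lies between them.

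Fourth, clinician review of notes, the multi-tier algorithm in section 9.9 and the rerun on validated cases all mitigate. They do so only in part, because section 9.7 also runs the models on all ICD-coded cases and Cohort 3 is only sampled for review.

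Two stronger readings are tempting. A reader might infer that the cohorts simply are not mutually exclusive. Overlap with Cohort 3 depends on how *most recent* is read; only the patient-level overlap of Cohorts 1 and 2 does not. A reader might also take 2% to 41%, or 3% to 30%, as an estimate of contamination. It is not one: the inputs are assumed, the notes requirement and the positive-test exclusion are ignored, and the protocol does not say which criteria the 240 already reflects.

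**Conclusion.** The point holds as an asymmetry in eligibility and an internal conflict. Controls are cleared of earlier myocarditis and cases are not, while Figure 1 implies that both should be. Following section 9.2.1 as written admits recoded disease to the ICD-based models and lets a patient such as D sit in two cohorts.

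This rests on reading the Cohort 1 and 2 index as the first code within the window, which is what section 9.1 says. If first-ever was meant, the problem disappears for those cohorts, but the text must say so.

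The direction of the bias for conditions that follow myocarditis is upward. Its size is unknown, and the counts and odds ratios above are illustrations under stated assumptions. The documents do not support saying that the cohorts are contaminated to any particular degree.

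**What to change.** In section 9.2.1, add to the case criteria for all three cohorts: no myocarditis code in EHR or claims before the index date, in all available look-back. Change the Cohort 3 index from the most recent to the first code; otherwise the new line contradicts it. Assign each patient to one cohort by first-ever code. Align sections 9.1 and 9.2.1 and Figure 1 accordingly. Because this changes how cases are defined, it belongs in the protocol as well as in the SAP.

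The cost is one eligibility line, one changed index rule and a filter on data already held. Case counts will fall somewhat, and recurrent myocarditis is described separately rather than modelled. Little is lost by that: since no control may have earlier myocarditis, the present design cannot give a usable odds ratio for it. Disease treated before a patient entered a contributing health system will still be missed, as section 9.9 acknowledges.

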#### 9.2.2. Exclusion criteria

Patients meeting any of the following criteria will not be included in the study:

1. Less than 365 days between the first recorded date a patient had activity of any kind recorded the Optum EHR database and a patients first recorded ICD code of myocarditis based on the cohort criteria above, or the index date for the controls.

Relevant codes/operational criteria for this study will be documented in an SAP, which will be dated, filed and maintained by the sponsor.

#### 9.3. Variables

As described above, patients in the myocarditis cohorts will be identified via ICD codes in the EHR data, and a subset will be confirmed using Brighton Collaboration criteria  and medical record review. The main study variables of interest, including demographics, diagnostic, therapeutic and laboratory/examinations are listed in **Table 1: Variables and associated roles.** Operational definitions, codes, more detailed listings of comorbidities, procedures and treatments, as well as any additional variables will be provided in the SAP.

Table 1. Variables and Associated Roles (Detailed Operationalization to be Described in SAP)

Variable	Role
Year of birth	Demographic
Sex	Demographic
Race/Ethnicity	Demographic
Geographic region (census regions)	Demographic
Payer type	Demographic
Date of matched encounter (index date for controls)	Index
Date of qualifying myocarditis diagnosis (index date for cases)	Diagnosis and index
Age at time of diagnosis (e.g., index date, or if unavailable then age entered or calculated in database closest to myocarditis diagnosis)	Diagnosis

Variable	Role
Time to diagnosis (time from first Optum EHR record until first myocarditis diagnosis date)	Diagnosis
Time since diagnosis (time from first myocarditis diagnosis date until last date in the Optum EHR or date of death)	Diagnosis
Laboratory biomarkers if feasible (e.g. troponin, CRP, CK-MB, CPK, additional lab markers TBD)	Diagnosis
Imaging* (e.g. echocardiogram, Cardiac MRI, Cardiac Magnetic Resonance, cMR, ECG)	Diagnosis
Procedures* (Biopsy / cardiac biopsy)	Diagnosis
mRNA COVID-19 vaccination	Exposure
SARS-CoV-2 infection	Exposure
Medical comorbidities prior to diagnosis/index date** (e.g. Charlson categories, Feudtner Complex chronic conditions [CCC] for pediatric populations, Healthcare Cost and Utilization Project Clinical Classifications Software [HCUP CCS] groups, incl. cardiac, immune, inflammatory conditions)	Medical history
Treatments prior to diagnosis/index date* (e.g. prior cardiac or COVID-related treatments, frequency of other drug classes)	Medical history
Procedures prior to diagnosis/index date* (e.g. cardiac, HCUP CCS groups)	Medical history
Labs of interest prior to diagnosis/index date* (e.g. labs mentioned above, as well as other cardiac labs, basic metabolic panel, complete blood count, urinalysis, thyroid test, lipid panel, cultures)	Medical history
Prior HCU within the 6 months prior to diagnosis/index date (e.g. hospitalizations, emergency department, other outpatient visits)  * Populs of these tests will not be available, only whether the results support	Medical history

\* Results of these tests will not be available, only whether the results supported the Brighton Criteria.

#### 9.4. Data sources

Optum's Electronic Health Record (EHR) and Integrated Claims-Clinical dataset, which combines adjudicated claims data (where available) with Optum's EHR data, are the data sources for this study. Optum integrates EHR data with claims, prescribing, dispensing, and practice management data by partnering directly with several multi-specialty medical groups, IDNs and hospital chains to extract data from their EHR and various information technology systems in the US. By normalizing, validating, and aggregating the de-identified data, Optum generates a longitudinal view of patient care.

Optum's longitudinal EHR repository is derived from dozens of healthcare provider organizations in the US, that include more than 57 contributing sources and 111K sites of care: treating more than 106 million patients receiving care in the US. The data is certified as de-identified by an independent

\*\* Detailed variables within each and relevant codes/operational criteria for each will be documented in a SAP, which will be dated, filed and maintained by the sponsor.

statistical expert following HIPAA statistical de-identification rules and managed according to Optum® customer data use agreements. Clinical, claims and other medical administrative data is obtained from both Inpatient and Ambulatory EHRs, practice management systems and numerous other internal systems. Information is processed, normalized, and standardized across the continuum of care from both acute inpatient stays and outpatient visits. Optum® data elements include demographics, medications prescribed and administered, immunizations, allergies, lab results (including microbiology), vital signs and other observable measurements, clinical and inpatient stay administrative data and coded diagnoses and procedures. In addition, Optum® uses natural language processing (NLP) computing technology to transform critical facts from physician notes into usable datasets. The NLP data provides detailed information regarding signs and symptoms, family history, disease related scores (i.e. RAPID3 for RA, or CHADS2 for stroke risk), genetic testing, medication changes, and physician rationale behind prescribing decisions that might never be recorded in the EHR.

Diagnosis data, laboratory data, and surgical procedure data for the study period of interest will be first be obtained from structured data (via International Classification of Diseases, Ninth Revision/Tenth Revision, Clinical Modification [ICD-9-CM/ICD-10-CM], International Classification of Diseases, Ninth Revision/Tenth Revision, Procedure Classification System [ICD-9-PCS/ICD-10-PCS], or Current Procedure Terminology (CPT) codes where applicable. Drug treatment data may also be pulled from prescription written, medication administration, and procedure tables when appropriate (via ICD-9-CM/ICD-10-CM, National Drug Center [NDC], CPT, and Healthcare Common Procedure Coding System [HCPCS] codes where applicable). In addition, Optum will use data available in the medical records for a subset of myocarditis patients that have clinical patient notes and other data that cannot be mapped into the larger structured database. These data may contain verbatim medical data, including text-based descriptions of medical information, such as medical records, physician notes, neurological scans, X-rays, or narrative fields in a database. When possible/appropriate, for validation of myocarditis diagnoses and analyses of risk factors and background epidemiology, lab data will also be used to augment the structured electronic health data.

### 9.5. Study size

This is a NI study with no *a priori* hypotheses specified; therefore, sample size calculations are not applicable. Based on initial feasibility assessment of the Optum EHR database, there were approximately 240 myocarditis cases within 21 days of mRNA vaccination, 1,730 myocarditis cases after SARS-CoV-2 infection, and 7,200 myocarditis cases prior to 01 November 2019. In addition, the large size of the database will allow for matching of each myocarditis case with controls for the risk factor analyses.

 CFR 164.514(b)(1).

<sup>[2] Guidance Regarding Methods for De-identification of Protected Health Information in Accordance with the Health Information Insurance Portability and Accountability Act (HIPAA) Privacy Rule (Dated as September 4, 2012, as first released on November 26, 2012).

## 9.6. Data management

Two major data sources for this study are described in greater detail in various sections throughout the protocol. Their collection, retrieval, preparation, and storage are summarized as follows:

1) Optum's EHR database: The EHR Database is a longitudinally linked structured data source. It has been formally de-identified by an independent statistical expert following HIPAA statistical de-identification rules and managed according to Optum® customer data use agreements. The EHR includes structured fields rendered by NLP technology, wherein Optum data experts mine provider notes and then normalize, validate, and integrate them into the electronic database.

In addition to these structured data, Optum has clinical notes available from some EHR systems and is able to use technology to search the verbatim text for phrases of interest and extract a small portion of those notes for review and clinical assessment. All data elements from this source are stored on Optum's firewalled, password-protected database. These data can only be extracted by approved Optum study personnel using standard and commercially available software (e.g., SAS, SQL, Python).

Optum's Integrated Claims-Clinical database: The EHR will be supplementally linked to
patients in Optum's Integrated Claims-Clinical adjudicated claims database. For a subset of
these patients, electronic clinical notes will undergo manual clinician review to confirm
myocarditis cases.

For the validation process using the electronic clinical notes (which will be converted to deidentified structured data for analyses), the Optum Natural Language Programming (NLP) team will determine if clinical notes are available for all qualifying patients with post-vaccine myocarditis, all qualifying post-SARS-CoV-2 infection myocarditis, as well as random samples of myocarditis diagnosed pre-2020. Optum will perform a series of "enhanced search" queries on the patient notes to determine key term content. Next, the Optum NLP team will use the key terms to extract note snippets into a file for review by the Optum Clinical team. These notes snippets will then be used to validate myocarditis cases per the Brighton Collaboration Criteria that were identified in the EHR using the inclusion and exclusion criteria specified in Section 9.2. After clinical review of the notes involving two clinicians from Optum, and categorization of the content for analysis, the resulting table of criteria will be created. The myocarditis cases will then be classified as validated or not validated, and relevant information entered into a spreadsheet that will serve as the data collection tool. Finally, the Optum clinical review team will provide these results of the case validation to the Optum Health Economics and Outcomes Research (HEOR) analytics team, whose members will identify matched controls for each case and conduct the multivariable analyses to assess risk factors for myocarditis

 CFR 164.514(b)(1).

 Guidance Regarding Methods for De-identification of Protected Health Information in Accordance with the Health Information Insurance Portability and Accountability Act (HIPAA) Privacy Rule (Dated as 04 September 2012, as first released on 26 November 2012).

using the structured data. This information will also be used to calculate the PPV of the algorithm used to initially identify the myocarditis cases in the structured EHR database.

Data will be transferred from the clinical review team to Optum's HEOR team via standard Data Transfer API (application programming interface). Extraction, merging, and cleaning of EHR and NLP-rendered data will be performed and adjudicated by at least two HEOR programmers and two HEOR analysts/directors. All data steps and code locations are formally documented in a data dictionary and are reviewed by the directing analyst and researcher before commencement of programming.

The Optum database is regularly updated. The date and version of the database will be specified in the report of the cohort, and any intermediate datasets will be archived as necessary for these results that will be submitted to a regulatory agency or published.

All analyses for this study will be conducted in SAS (version 9.4 or higher, SAS Institute, Cary, NC, US).

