# 8. RESEARCH QUESTION AND OBJECTIVES

The objective of this study is to characterize risk factors for myocarditis in the following three cohorts: 1) myocarditis diagnosed post any type of mRNA COVID-19 vaccine, 2) myocarditis diagnosed post SARS-CoV-2 infection (2020-2022), or 3) myocarditis diagnosed prior to the COVID-19 era (pre-2020). To accomplish this objective, the study will characterize demographics, medical history, and comorbidities of patients with myocarditis prior to diagnosis during a baseline period and then examine risk factors for myocarditis using multivariable models. Myocarditis cases identified in the EHR or claims post-vaccine or post COVID-19 infection, as well as a sample of cases in the pre COVID era cohort, will be validated by clinicians using the Brighton Collaboration criteria  applied to review of medical records at Optum as the gold standard. Using those validated cases, the study will also assess and compare the PPV for the myocarditis definitions based on codes for the three cohorts in the Optum deidentified EHR data.

Among patients diagnosed with myocarditis in the deidentified Optum EHR data, the study specific objectives are detailed below.

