#### **Secondary objectives:**

- 1. To examine the risk factors in each myocarditis cohort stratified by age group at diagnosis, sex, time period and follow-up time (years).
- 2. To assess and compare the validity of myocarditis diagnosis case definitions in administrative data for each cohort, via calculating the PPV using electronic medical record review.

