# 9.8. Quality control

All codes and/or code algorithms will be reviewed by the Safety Risk Lead in the Safety Surveillance and Risk Management group for the Pfizer COVID-19 vaccine program, as well as the protocol authors. The ICD-9-CM and ICD-10-CM codes used in the study will be reviewed against relevant codes used in the Food and Drug Administration (FDA) Sentinel program whenever applicable; if there are any discrepancies, the Sentinel codes will be used unless there is a strong rationale to use internally developed ICD codes and/or ICD algorithms instead. Additional validation of the code lists will be performed if warranted. All efforts will be made to ensure quality and safe storing of data and reports. Quality control (QC) checks will be performed on all SAS programming, data tables, and reports generated in the course of this research. QC findings and documentation of remedial action will be maintained. Storage of programming, data, and reports will be carried out per standard procedures, and as specified in Section 9.6.

In the validation study, after the Optum NLP team creates key term tags for use in the snippet review for the two Optum clinicians who will review patient notes with these key terms mentioned, the two clinicians will record their findings from the notes regarding whether the notes support a myocarditis diagnosis based on the Brighton Criteria. These results will be provided to the HEOR team for review and any clarifications or questions will be managed between the two groups until resolved.

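### Case review allows only validated or not validated, so cases with too little information in the snippets lower the PPV and can create or mask a difference between cohorts

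*Protocol*

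**What the plan says.** Section 9.6 describes the review. After keyword searches of the notes, "the Optum NLP team will use the key terms to extract note snippets into a file for review by the Optum Clinical team". The same section says the data vendor holds notes from some EHR systems and can search them and "extract a small portion of those notes for review and clinical assessment". Two clinicians then assess the snippets against the Brighton criteria, and the outcome has two values: "The myocarditis cases will then be classified as validated or not validated". Later in the section: "This information will also be used to calculate the PPV of the algorithm used to initially identify the myocarditis cases".

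Section 9.8 has the same structure. The clinicians record "whether the notes support a myocarditis diagnosis based on the Brighton Criteria". Section 8 describes the Brighton criteria as "applied to review of medical records at Optum as the gold standard". Secondary objective 2 is "To assess and compare the validity of myocarditis diagnosis case definitions in administrative data for each cohort", by means of the PPV.

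Section 9.2.1 makes note availability an entry criterion. For Cohort 1, notes must be available for "confirmation of myocarditis post-mRNA COVID-19 vaccination thirty days before or after the index event"; Cohorts 2 and 3 have parallel criteria. No minimum number or content of notes is set.

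No section provides a category, or a rule, for a reviewed case with too little information to judge.

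**The concern.** A case can fail to be validated in two ways: the notes show that it was not myocarditis, or they do not say enough. Only the first is evidence against the code algorithm. A two-way label merges them, and the merged label feeds the PPV.

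Cases that cannot be judged are foreseeable from the protocol itself. Reviewers see extracts, not charts. The note criterion can be read as met by notes from before the diagnosis alone. Section 7 says that biopsy is used infrequently, and Section 9.9 accepts that laboratory data may be incomplete.

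The share of such cases could also differ between cohorts. Section 9.1 indexes Cohorts 1 and 2 on the first myocarditis code but Cohort 3 on the most recent one. A most recent code may be a follow-up contact, with the acute work-up outside the 30-day note window. This is an inference from the design, not data.

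Two results depend on the label: the PPV comparison, and the risk-factor models that Section 9.7 runs on validated cases.

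**Working it through.** The protocol states no expected PPV, precision target or insufficient share, so there is no figure of its own to reproduce. The check is an illustration.

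**Inputs**
- Review outcome: two categories (Section 9.6).
- Feasibility counts: about 240 cases in Cohort 1 and 1,730 in Cohort 2 (Section 9.5). Section 9.6 considers all qualifying cases in these two cohorts for review, and random samples of unstated size in Cohort 3.
- Assumed: true PPV *P*; share *u* of reviewed cases with insufficient information, independent of true status.

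**Formula.** If insufficient cases are labelled not validated and stay in the denominator, observed PPV = *P* × (1 − *u*).

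**Same true PPV, 80%, in two cohorts A and B**

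| *u*, A vs B | A | B | False gap |
|---|---|---|---|
| 5% vs 10% | 0.80 × 0.95 = 76% | 0.80 × 0.90 = 72% | 4 points |
| 5% vs 15% | 76% | 0.80 × 0.85 = 68% | 8 points |
| 10% vs 35% | 0.80 × 0.90 = 72% | 0.80 × 0.65 = 52% | 20 points |
| 20% vs 20% | 0.80 × 0.80 = 64% | 64% | 0 |

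The gap is *P* × (*u*B − *u*A). For 5% vs 15% it is 0.60 × 0.10 = 6 points at a true PPV of 60%, and 0.90 × 0.10 = 9 points at 90%.

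**Masking.** Let the true PPVs be 80% and 60%, with insufficient shares of 30% and 5%. Observed: 0.80 × 0.70 = 56% and 0.60 × 0.95 = 57%. A true 20-point difference disappears.

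**Equal shares, different true PPVs.** With 80% vs 60% and *u* = 20%, observed PPVs are 64% and 48%. The difference shrinks from 20 to 16 points; the ratio stays 1.33.

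**Chance of a false significant result**, two-sided 5%, taking 240 and 1,730 reviewed cases with the smaller *u* in Cohort 1. For 76% vs 68%, the pooled standard error is about 0.0319 and the unpooled about 0.0298. Power = Φ[(0.08 − 1.96 × 0.0319) / 0.0298] ≈ Φ(0.59) ≈ 72%. For 76% vs 72% the same calculation gives about 25%.

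**What a third category would show.** Take 240 reviewed cases with 168 confirmed (assumed numbers).

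| Insufficient | Counted as false | Excluded | Counted as true |
|---|---|---|---|
| 24 | 168/240 = 70.0% | 168/216 = 77.8% | 192/240 = 80.0% |
| 48 | 70.0% | 168/192 = 87.5% | 216/240 = 90.0% |

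The planned two-way label reports 70.0% in both rows.

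Applied to the 5% vs 15% example, the three versions give 76% vs 68%, then 0.76/0.95 = 80% vs 0.68/0.85 = 80%, then 76 + 5 = 81% vs 68 + 15 = 83%. The false gap closes and then reverses, so it would not be mistaken for a real one.

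**The case against.** **The denominator is not written out.** The protocol nowhere says that unclassifiable cases count as false positives. A table of criteria and other information also go into the data collection tool, and Section 9.7 leaves detailed methods to the SAP, which is not at hand and could exclude such cases. This stands as a limit on the wording: the treatment follows from a two-way label but is not stated. It does not remove the point, because the SAP can only separate what reviewers recorded. The footnote to Table 1 in Section 9.3 says that for imaging, biopsy and other starred items only support for the Brighton criteria will be available. A test not done may then look the same as a negative one.

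**Bias in the comparison is conditional.** A reader might infer that the cross-cohort comparison is biased as planned. The documents do not support that. A false gap needs unequal insufficient shares, and no section shows that documentation differs by cohort.

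**There are safeguards.** Every cohort requires notes around the index date, and cases need an inpatient record or two records at least 30 days apart. The 30-day window may also be meant to cover both sides of the index. These criteria remove cases with no notes, but not cases with uninformative snippets.

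**Dropping insufficient cases is not neutral either.** Section 9.9 warns of rule-out and historical codes. Such codes may be both false and poorly documented, and excluding them would inflate the PPV. This stands: confirmed divided by confirmed plus refuted should not be presented as the unbiased answer.

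**The risk-factor models are less exposed.** Section 9.7 also fits them to all code-identified cases. Losing true cases from the validated set costs precision; it biases odds ratios only if the loss is related to the risk factors.

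**Conclusion.** The point holds in conditional form. The protocol fixes a two-way label from note extracts, uses it for the PPV and provides no place for cases that cannot be judged. Followed as written, this lowers each cohort's PPV by the factor 1 − *u* when insufficiency is unrelated to true status. It can create or mask a cohort difference when *u* differs.

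At an assumed true PPV of 80%, the false gap is 4 points for shares of 5% vs 10%, 8 points for 5% vs 15%, 20 points for the wide pair of 10% vs 35%, and zero for equal shares. All the shares and the true PPV are assumptions. If insufficiency depends on true status, these figures change, but the range from counting all such cases as false to counting all as true still contains the PPV, provided the confirmed and refuted calls are correct.

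**What to change.** In Section 9.6 and the data collection tool, have the clinicians classify each case at review as confirmed, refuted or insufficient information. Recording this at review is safer than deriving it later, given the Table 1 footnote. Align the wording of Section 9.8.

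Report for each cohort:
- the share with insufficient information;
- the PPV with these cases counted as false, excluded, and counted as true.

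Call a cross-cohort PPV difference real only if it holds in all three versions. No single version need be declared the unbiased primary one.

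The cost is one field on a form that Section 9.6.1 already requires for each adjudicated patient, and a reported range instead of one figure. No extra reviewers are needed if the field is in place at review. If review is already complete, cases labelled not validated may need a second look; Section 5 lists case adjudication among past vendor delays, so this should be settled early.
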